11.7.4. DATA ANALYSIS

11.7.4.1. Sample Size Expectations

The objectives of this ancillary study are exploratory (not confirmatory) in nature and not intended to be sufficiently powered to confirm a pre-determined level of sensitivity and specificity. The number of sites and subjects that will participate in the ancillary study depends upon the outcome of the site EHR capabilities assessment described in Section 11.7.3.2 (Site Selection). Five study sites recruiting 12-15 subjects each would enable a descriptive assessment of Objectives 1 and 2, whilst, if feasible, 500-1000 subjects at EHR-enabled sites would permit greater precision to be achieved in the assessment of Objective 3.

11.7.4.2. Objective 1: Assess the Barriers to Using as EHR-Generated List of Patients to Facilitate Trial Enrollment

Because any survey administered for this objective will be a site-level survey, analysis of the survey data will be performed across all sites. For quantities of interest, frequencies with percentages for categorical measures and means with standard deviations for continuous measures will be presented.

11.7.4.3. General Analytic Approach for Objective 1 and Objective 2

The goals of both Objective 2 and Objective 3 involve evaluating the performance of algorithms that map EHR-based data into concepts present in the clinical trial dataset. The actual measures recorded in the clinical trial dataset will be considered the reference standard against which these algorithm-based measures are compared.

Table 4 Overall performance of EHR-based algorithms for baseline characteristics, using clinical trial data as the reference standard / Categorical variables

| New measure (EHR Ancillary Study data) | Reference standard (Clinical trial data) | |
|---|---|------------------------|
| | Condition present | Condition absent |
| Condition present | True positive (TP) | False positive (FP) |
| Condition absent | False negative (FN) | True negative (TN) |

For categorical variables, estimated performance metrics will be based on the 2x2 cross-tabulation of values in the EHR Ancillary Study dataset with values in the clinical trial dataset (Table 4) and include:

- Overall agreement = $(TP + TN) / (TP + FP + FN + TN)$
- Sensitivity = $TP / (TP + FN)$

- Specificity = $TN / (FP + TN)$
- Positive predictive value = $TP / (TP + FP)$
- Negative predictive value = $TN / (FN + TN)$
- Accuracy or efficiency = $(TP + TN) / (TP+TN+FP+FN)$

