| To evaluate (at a subset of sites) barriers to using the electronic health record (EHR) to facilitate trial enrolment and the quality of EHR data for use in populating baseline characteristics and identifying events of interest during trial follow-up. ² | 
 Workflow impact of an EHR-generated list of subjects to facilitate trial enrolment. Concordance, sensitivity, specificity, and accuracy of baseline characteristics extracted from the EHR compared with those reported on the electronic case report form (eCRF)³ Concordance, sensitivity, specificity, and accuracy of EHR-identified events compared with study events ^{3,4} |

1. If the primary endpoint meets the criteria for non-inferiority, a multiple comparisons adjustment strategy will be performed for these 3 secondary endpoints as specified in the Section 8.3.5.
2. Details are provided in a separate EHR ancillary study protocol (Appendix 7). Results from this exploratory investigation will be reported separately from the main clinical study report.
3. Comparison of EHR identified events with study events will be conducted in the same data subset.
4. Analyses to be undertaken after the main trial results are published.

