11.7.2. Ancillary Study OBJECTIVES

11.7.2.1. Primary Objectives

Objective 1: Assess the barriers to using an EHR-generated list of patients to facilitate trial enrollment.

Through site study coordinator surveys, workflow assessment, analysis of electronic screening logs, comparisons of enrolled patients with patients identified via algorithm, this retrospective objective will describe the screening “funnel” and identify factors responsible for narrowing the funnel from the pool of potentially eligible patients to those enrolled in the clinical trial. Barriers for using EHR systems for this purpose will be assessed at the site level and common cross-site themes will be identified.

Objective 2: Evaluate the fitness of EHR data for use in populating the baseline characteristics in the eCRF

After study completion and within selected data areas (e.g., demographics, medical history, concomitant medications), the level of agreement between data extracted from the EHR and data documented on the baseline eCRF (reference standard) will be evaluated. Additionally the performance of algorithms developed to identify comorbidities and other clinical concepts will be assessed at the site level and aggregated, where appropriate.

Objective 3: Explore the use of EHR data to find events of interest during trial follow-up

Case-finding algorithms will be developed for select specified endpoints (i.e., myocardial infarction, stroke, unstable angina, heart failure as outlined in the main study protocol), run during the conduct of the trial, and used to identify potential cases for follow-up by the study coordinator. The site study coordinator will record the dispensation of each potential case so that reconciliation can occur between eCRF documented events and EHR-generated potential events. Safety event reporting will proceed as outlined in the main study protocol (Main Protocol Section 6.2). At the conclusion of the study, the yield of case-finding algorithms will be evaluated along with the performance of EHR-based algorithms with eCRF-reported as well as adjudicated eCRF-reported events (reference standard).

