11.7.4. DATA ANALYSIS

11.7.4.1. Sample Size Expectations

The objectives of this ancillary study are exploratory (not confirmatory) in nature and not intended to be sufficiently powered to confirm a pre-determined level of sensitivity and specificity. The number of sites and subjects that will participate in the ancillary study depends upon the outcome of the site EHR capabilities assessment described in Section 11.7.3.2 (Site Selection). Five study sites recruiting 12-15 subjects each would enable a descriptive assessment of Objectives 1 and 2, whilst, if feasible, 500-1000 subjects at EHR-enabled sites would permit greater precision to be achieved in the assessment of Objective 3.

11.7.4.2. Objective 1: Assess the Barriers to Using as EHR-Generated List of Patients to Facilitate Trial Enrollment

Because any survey administered for this objective will be a site-level survey, analysis of the survey data will be performed across all sites. For quantities of interest, frequencies with percentages for categorical measures and means with standard deviations for continuous measures will be presented.

11.7.4.3. General Analytic Approach for Objective 1 and Objective 2

The goals of both Objective 2 and Objective 3 involve evaluating the performance of algorithms that map EHR-based data into concepts present in the clinical trial dataset. The actual measures recorded in the clinical trial dataset will be considered the reference standard against which these algorithm-based measures are compared.

Table 3 Overall performance of EHR-based algorithms for baseline characteristics, using clinical trial data as the reference standard / Categorical variables

| New measure (EHR Ancillary Study data) | Reference standard (Clinical trial data) | |
|---|---|------------------------|
| | Condition present | Condition absent |
| Condition present | True positive (TP) | False positive (FP) |
| Condition absent | False negative (FN) | True negative (TN) |

For categorical variables, estimated performance metrics will be based on the 2x2 cross-tabulation of values in the EHR Ancillary Study dataset with values in the clinical trial dataset (Table 3) and include:

$$\text{Overall agreement} = (TP + TN) / (TP + FP + FN + TN)$$

$$\text{Sensitivity} = TP / (TP + FN)$$

$$\text{Specificity} = TN / (FP + TN)$$

Positive predictive value = $TP / (TP + FP)$

Negative predictive value = $TN / (FN + TN)$

Accuracy or efficiency = $(TP + TN) / (TP+TN+FP+FN)$

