For dichotomous measures, each of these proportions is immediately calculable. For measures having more than two levels, multiple dichotomous measures will be created in order to calculate these proportions. Confidence intervals (95%) will be reported around these quantities. (See [Table 4](#) as an example).

Table 4 Overall performance of EHR-based algorithms for baseline characteristics, using clinical trial data as the reference standard / Categorical variables

| Measure | Overall agreement (95% CI) | Sensitivity (95% CI) | Specificity (95% CI) | Positive predictive value (95% CI) | Negative predictive value (95% CI) |
|-----------|----------------------------|-----------------------|-----------------------|------------------------------------|------------------------------------|
| Measure 1 | xx.x (xx.x – xx.x) | xx.x (xx.x – xx.x) | xx.x (xx.x – xx.x) | xx.x (xx.x – xx.x) | xx.x (xx.x – xx.x) |
| Measure 2 | xx.x (xx.x – xx.x) | xx.x (xx.x – xx.x) | xx.x (xx.x – xx.x) | xx.x (xx.x – xx.x) | xx.x (xx.x – xx.x) |
| | | | | | |

Reported on 0–100 scale

For continuous measures, bias will be calculated as the difference between values in the EHR Ancillary Study dataset and values in the clinical trial dataset. The mean and standard deviation of the bias along with a 95% confidence interval will be reported. In Bland-Altman analyses of agreement between continuous measures, the standard deviation of the bias is referred to as the precision, while the 95% confidence interval is referred to as the limit of agreement. (See [Table 5](#) as an example).

Table 5 Overall performance of EHR-based algorithms for baseline characteristics, using clinical trial data as the reference standard / Continuous variables

| Measure | Bias | |
|-----------|-----------|----------|
| | Mean (SD) | 95% (CI) |
| Measure 1 | xx.x | xx.x |
| Measure 2 | xx.x | xx.x |
| | | |

Due to the nature of EHR data, it is expected that there will be systematic differences between sites with respect to coding of clinical concepts. All performance metrics will therefore initially be calculated by site. These site-specific results may be best reported graphically.

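### For baseline measures with more than two levels, the EHR ancillary study plans agreement only on derived dichotomies, so the share of subjects placed in the right level is not reported directly

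*Protocol*

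**What the plan says.** Objective 2 of the ancillary study (Section 11.7.2.1) is to judge whether EHR data are fit to populate the baseline eCRF. Its stated target is that "the level of agreement between data extracted from the EHR and data documented on the baseline eCRF (reference standard) will be evaluated".

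Section 11.7.4.3 gives the method: every categorical metric comes from a 2x2 table that sets the EHR value against the trial's own value. The list that follows contains overall agreement, sensitivity, specificity, positive and negative predictive value, and accuracy (also called efficiency). Overall agreement and accuracy are both defined as true positives plus true negatives over all four cells. For variables with more levels, "For measures having more than two levels, multiple dichotomous measures will be created in order to calculate these proportions", and "Confidence intervals (95%) will be reported around these quantities". The example table has columns for overall agreement, sensitivity, specificity and the two predictive values, but none for accuracy. Agreement and the other proportions are then carried into a hierarchical model for the average site.

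The section does not name the dichotomous coding, does not say that the dichotomies will be averaged, and plans neither agreement on the full k x k table nor kappa. The wording is the same in all three versions of the appendix in the file, including the one carrying Amendment 2. A footnote in Section 2 refers to Appendix 7 for the details of the ancillary study.

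**The concern.** For a field with k levels, fitness to populate the eCRF means first of all that the EHR supplies the right level. That is the proportion on the diagonal of the k x k table. The plan replaces this table with several 2x2 tables. In any one of them, a subject who is misclassified between two other levels counts as a true negative, and so as agreement. The overall agreement column can then look better than the field deserves, and more so as the number of levels grows. Fields with different numbers of levels also cannot be compared on that column.

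At stake is the readability of one descriptive result. A reader who takes the agreement column as the chance that a multi-level field is filled correctly would be too optimistic. Listing the same formula twice adds nothing to help that reader.

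**Working it through.** **Inputs.** From Section 11.7.4.3: agreement = (TP + TN) / (TP + FP + FN + TN), applied to dichotomies of any measure with k > 2 levels. The protocol gives no k and no error rate. Assumed here: a share A = 0.80 of subjects in the right level, so a misclassification rate m = 1 - A = 0.20, with k from 2 to 6 shown as a range. There is no plan figure to reproduce.

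**1. Direction, whatever the coding.** A dichotomy that keeps all subjects is a yes/no function of the level. A subject with the same level in both sources gets the same yes/no in both. Hence agreement on every such dichotomy is at least A. It equals A only if every misclassified subject crosses that particular cut.

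**2. Size under one-versus-rest coding.** A misclassified subject is a false negative in the table for the true level, a false positive in the table for the assigned level, and a true negative in the other k - 2. The k error rates therefore sum to 2m. Their mean is 2m/k, and mean agreement is 1 - 2(1 - A)/k. Over 5,000 random k x k tables (k from 2 to 7) the identity held to rounding, with a largest deviation of about 1e-16.

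| k | Right level (diagonal/N) | Mean one-versus-rest error | Mean one-versus-rest agreement |
|---|---|---|---|
| 2 | 80.0% | 0.200 | 80.0% |
| 3 | 80.0% | 0.133 | 86.7% |
| 4 | 80.0% | 0.100 | 90.0% |
| 5 | 80.0% | 0.080 | 92.0% |
| 6 | 80.0% | 0.067 | 93.3% |

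**3. A single dichotomy need not show the factor 2/k.** Two examples with k = 4, m = 0.20 and 1,000 subjects:
- All errors between levels 1 and 2: error rates 0.20, 0.20, 0 and 0. Two tables show the full rate and two show none.
- All errors are assignments to level 1: error rates 0.20, 0.08, 0.07 and 0.05.

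In both, the sum is 0.40 = 2m and the mean is 0.10 = 2m/4.

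**4. Another coding.** With cumulative cuts, k = 4 and evenly spread errors, the error rates are 0.100, 0.133 and 0.100, with mean 0.111. This again lies below 0.20, but is not 2m/k.

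**5. The neighbouring columns.** With balanced levels and errors, sensitivity and positive predictive value stay at 0.80 for every k. Specificity and negative predictive value do rise with k: 0.80 (k = 2), 0.933 (k = 4), 0.96 (k = 6). In the second example of step 3, agreement for levels 2 to 4 is 0.92, 0.93 and 0.95, beside sensitivities of 0.556, 0.462 and 0.444. Under one-versus-rest coding A can be rebuilt as the sum of the k true-positive counts over N. There, (600 + 100 + 60 + 40)/1000 = 0.80.

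**6. The duplicate.** The two formulas for overall agreement and accuracy have the same numerator and the same four cells in the denominator. They give one number.

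**The case against.** The strongest reply is that nothing the plan says it will report is incorrect. Each agreement figure is right for its own yes/no question, and no average over dichotomies is planned, so 2/k describes a summary that the protocol does not produce. One-versus-rest coding is itself an inference. Sensitivity and positive predictive value stand in the same table with confidence intervals and show the misclassification. The design is mostly framed around conditions that are present or absent, no multi-level variable is listed, and the work is "exploratory (not confirmatory) in nature and not intended to be sufficiently powered to confirm a pre-determined level of sensitivity and specificity". All of this stands, and it limits the point.

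Three stronger readings are tempting, and the documents do not support them:
- That the plan's agreement figures are biased upward by 2/k. They are not biased for the dichotomies they describe, and the factor holds only for an unplanned mean under an unstated coding.
- That nothing in the plan would expose the problem. Sensitivity and positive predictive value would.
- That two of the Section 2 endpoints are the same number. Section 2 lists "Concordance, sensitivity, specificity, and accuracy of baseline characteristics extracted from the EHR", but concordance is nowhere defined. Only the two formulas in Section 11.7.4.3 are shown to be identical.

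The reply does not remove the gap. The target is agreement on the baseline characteristic, and the reader must reassemble it from several rows. The neighbouring columns may also be weak for rare levels. Five sites of 12 to 15 subjects give 60 to 75 subjects. A level held by an assumed 3% then has about 2 of them, and a sensitivity of 1/2 has an exact 95% CI of about 1% to 99%. Nor is this merely a detail left to an analysis plan, because the appendix states the method.

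**Conclusion.** The point holds in limited form. For measures with more than two levels, Section 11.7.4.3 calculates overall agreement only on derived dichotomies. Provided each dichotomy keeps all subjects, every such figure is at or above the share of subjects in the right level, and that share is not itself a planned output. Under one-versus-rest coding the average shortfall in visible error is exact: the mean error is 2/k of the true rate, so an assumed 80% would read 86.7% at k = 3 and 92.0% at k = 5 if averaged. The 80%, the values of k and the coding are assumptions. The direction does not depend on them.

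The statement concerns the agreement figure (and accuracy, its duplicate), not the whole assessment of fitness. Priority is minor. The ancillary study is exploratory, no level of agreement decides fitness, its results are reported separately from the main study report, and no conclusion of the main trial is touched.

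**What to change.** In Section 11.7.4.3:
- For a measure with k > 2 levels, report overall agreement once, as the number of subjects on the diagonal of the k x k table divided by N, with its 95% CI. Use the same match/no-match indicator in the hierarchical model for agreement.
- Name the coding of the dichotomies and keep them for level-specific sensitivity, specificity and predictive values.
- Delete accuracy as a separate metric, since it repeats overall agreement. If a second measure is wanted, a chance-corrected one such as Cohen's kappa (weighted for ordered levels) could take its place. This is optional. Align the Section 2 endpoint wording by saying what concordance means.

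The cost is a sentence or two of text and a few lines of code. No new data are needed. The agreement reported for multi-level fields will read lower than the dichotomised figures or, at most, equal to them.
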